### Order of Administration

Mirvetuximab soravtansine should be administered first, followed by pembrolizumab.

#### **Caregiver Precautious**

Mirvetuximab soravtansine is an experimental anticancer drug, and, as with other potentially toxic compounds, caution should be exercised when handling this compound. It is recommended that gloves and protective garments be worn during preparation and clean-up of any spills or bodily fluids from a patient treated with mirvetuximab soravtansine. Refer to Section 8.1 and package inserts for more information.

### 5.3.2 Pembrolizumab (MK-3475)

Dosing

Pembrolizumab 200 mg as a 30 minute infusion on Day 1 of each 21-day cycles

Sites should make every effort to target infusion timing to be as close to 30 minutes as possible. However, given the variability of infusion pumps from site to site, a window of -5 minutes and +10 minutes is permitted (i.e., infusion time is 30 minutes: -5 min/+10 min).

#### Drug, Tubing and Filtration

The liquid drug product (DP) can be diluted with normal saline or 5% dextrose in the concentration range of 1 to 10 mg/mL in IV containers made of material listed in Section 8.2.7. Section 8.2.7 contains specific instructions for the preparation of the pembrolizumab infusion fluid and administration of infusion solution.

#### Infusion Reactions

Infusion-related reactions have been reported with pembrolizumab, and are non-immunemediated events.

Pembrolizumab may cause severe or life threatening infusion-reactions including severe hypersensitivity or anaphylaxis. Signs and symptoms usually develop during or shortly after drug infusion and generally resolve completely within 24 hours of completion of infusion. Dose modification and toxicity management guidelines on pembrolizumab associated infusion reaction are provided in Table 2.

CTCAE v5.0 Severity Grade	Treatment	Premedication at Subsequent Dosing
Grade 1 Mild reaction: infusion interruption	Increase monitoring of vital signs	None
not indicated: intervention not	narticipant is deemed medically	
indicated	stable in the opinion of the	
	investigator.	
Grade 2	Stop Infusion.	Participant may be premedicated
Therapy or infusion interruption	Additional appropriate medical	$1.5h (\pm 30 \text{ minutes}) \text{ prior to}$
indicated but responds promptly to	therapy may include but is not	infusion of pembrolizumab with:
symptomatic treatment (e.g.,	limited to:	Diphenhydramine 50 mg po (or
antihistamines, NSAIDs, narcotics,	IV fluids	equivalent dose of antihistamine).
IV fluids); prophylactic	Antihistamines	Acetaminophen 500-1000 mg po
medications indicated for $\leq 24$ hrs	NSAIDs	(or equivalent dose of analgesic).
	Acetaminophen	
	Narcotics	
	Increase monitoring of vital signs	
	as medically indicated until the	
	participant is deemed medically	
	stable in the opinion of the	
	investigator.	
	If symptoms resolve within 1 hour	

### Table 2: Management Guidelines for Potential Pembrolizumab Infusion-related Reactions

	of stopping drug infusion, the infusion may be restarted at 50% of the original infusion rate (e.g. from 100 mL/hr to 50 mL/hr). Otherwise dosing will be held until symptoms resolve and the participant should be premedicated for the next scheduled dose. Participants who develop Grade 2 toxicity despite adequate premedication should be permanently discontinued from further study drug treatment	
Grades 3 or 4	Ston Infusion.	No subsequent dosing
Grade 3:	Additional appropriate medical	The succeducit dooling
Drolonged (i.e. not ranidly	therapy may include but is not	
romongius to sumptometic	limited to:	
responsive to symptomatic	Eninentaria e**	
medication and/or brief interruption	Epinephrine**	
of infusion); recurrence of	IV fluids	
symptoms following initial	Antihistamines	
improvement; hospitalization	NSAIDs	
indicated for other clinical sequelae	Acetaminophen	
Grade 4:	Narcotics	
Life-threatening consequences,	Oxygen	
urgent intervention indicated	Pressors	
	Corticosteroids	
	Increase monitoring of vital signs	
	as medically indicated until the	
	participant is deemed medically	
	stable in the opinion of the	
	investigator	
	Hospitalization may be indicated	
	**In cases of anaphylaxis	
	eninenhrine should be used	
	immediately	
	Doution on t is norman and the	
	r ar ucipant is permanently	
	discontinued from further study	
	drug treatment.	
Appropriate resuscitation equipment shou	ld be available at the bedside and a physicia	an readily available during the period of
drug administration.		

For further information, please refer to the Common Terminology Criteria for Adverse Events v5.0 (CTCAE) at http://ctep.cancer.gov/protocolDevelopment/electronic\_applications/ctc.htm.

## Order of Administration

Mirvetuximab soravtansine should be administered first, followed by pembrolizumab.

#### 5.4 General Concomitant Medication and Supportive Care Guidelines

All concomitant medications, over-the-counter, herbal supplements and supportive therapy taken within 28 days of Cycle 1, day 1 and through 30 days after last study treatment must be recorded on the appropriate eCRF. The identity of all medications, dosage, and route of administration,

frequency, duration of administration, and indication for use will be recorded in the appropriate sections of the eCRF.

# 5.4.1 Required Supportive Care Medications

## 5.4.1.1 Premedications

All patients must receive 325-650 mg of acetaminophen/paracetamol (PO or IV), 10 mg IV dexamethasone, and 25-50 mg diphenhydramine (PO or IV)(equivalent drugs of similar drug classes is also acceptable) approximately 30-90 minutes prior to each infusion of mirvetuximab soravtansine. If individual patients require more intensive treatment to prevent infusion-related reactions, investigators may modify the regimen accordingly.

# 5.4.1.2 Eye drops

Lubricating artificial tears and corticosteroid eye drops are mandatory for all patients receiving mirvetuximab soravtansine as follows (Appendix D):

- Patients are required to use corticosteroid eye drops as prescribed by the treating physician unless the risk outweighs the benefit as per the ophthalmologist/physician. All patients enrolled will be instructed to self-administer 1% prednisolone (Pred Forte® or generic equivalent) six times daily on Days 1-4 and four times daily on Days 5-8 of each cycle during the study. For individual patients who cannot tolerate the preservative contained in 1% prednisolone, other corticosteroid eye drops may be substituted (e.g. difluprednate 0.05%; Durezol®) and administered on Days 1-8 of each cycle at a frequency prescribed by the ophthalmologist.
- Patients will be required to use preservative-free, lubricating artificial tears on a daily basis (as directed by the product label or the treating physician). Patients should be advised to wait at least 15 minutes following steroid administration before instilling lubricating eye drops.
- The patient should continue use of the corticosteroid eye drops per the ophthalmologist recommendation after discontinuation of mirvetuximab soravtansine. The patient should continue the lubricating eye drops for 4 weeks following discontinuation of mirvetuximab soravtansine.

## 5.4.2 Other supportive care

- Antiemetic (e.g. 5-HT3 serotonin receptor antagonists such as palonosetron, granisetron or ondansetron), antidiarrheal (e.g. loperamide) medications, and other supportive care may be used at the discretion of the treating physician, unless prohibited below in Section 5.4.3.
- Patients are strongly advised to avoid using contact lenses while on mirvetuximab soravtansine.

- Baby shampoo and a soft cloth should be used to clean the eyes, and a warm compress at bedtime may be used to decrease any possible inflammation on the eyelid's surface.
- The use of UVA/UVB sunglasses is recommended in full daylight during the course of the study.
- The use of temporary lower punctal plugs to increase lubrication of the eyes is optional if lubricating artificial tears and corticosteroid eye drops are not sufficient.

The management and dose modification for ocular symptoms is outlined in Section 6.

# 5.4.3 Prohibited Medications

Potent CYP3A4 inhibitors such as ketoconazole and erythromycin should be avoided during study treatment. *In vitro* metabolism studies demonstrated that DM4 is predominantly metabolized by thiol s-methyltransferase (TMT) to form Me-DM4, which is further metabolized into sulfoxide-methyl-DM4. As Me-DM4 has been shown to be primarily metabolized by CYP3A, its exposure could potentially be increased in the presence of strong CYP3A inhibitors. Drinking greater than 1 serving (250 mL) of grapefruit juice per day should be avoided.

In addition, participants are prohibited from receiving the following therapies during Screening and Treatment phase of the trial

- Antineoplastic systemic chemotherapy or biological therapy
- Immunotherapy not specified in this protocol
- Investigational agents other than the study drugs
- Folate-containing vitamins
- Growth factors (G-CSF, GM-CSF) cannot be used during cycle 1, but are allowed on subsequent cycles of treatment as per published ASCO or institutional guidelines.
- Available in vitro metabolism data suggest DM4 has a potential to inhibit CYP3A activity *in vivo*. The risk of a significant in vivo drug-drug interaction caused by DM4 inhibition of CYP3A is not currently known, therefore, treatment of patients with concomitant medications that are sensitive substrates of CYP3A or are CYP3A substrates with a narrow therapeutic index should be carefully monitored.
- Grapefruit juice and or the oral consumption of grapefruit should be avoided.
- Live vaccines within 30 days prior to the first dose of study treatment and while participating in the study. Examples of live vaccines include, but are not limited to, the following: measles, mumps, rubella, varicella/zoster, yellow fever, rabies, BCG, and typhoid vaccine. Seasonal influenza vaccines for injection are generally killed virus

vaccines and are allowed; however, intranasal influenza vaccines (eg, FluMist®) are live attenuated vaccines and are not allowed.

- Systemic glucocorticoids for any purpose other than to modulate symptoms from an event of clinical interest of suspected immunologic etiology. The use of physiologic doses of corticosteroids may be approved after consultation with the Overall PI.
- Contact lens use should be avoided during study treatment period

# 5.5 Criteria for Taking a Participant Off Protocol Therapy

Duration of therapy will depend on individual response, evidence of disease progression and tolerance. In the absence of treatment delays due to adverse event(s), treatment with both agents may continue for up to 35 doses (approximately 2 years), or with mirvetuximab soravtansine alone after 35 cycles, or until one of the following criteria applies:

- Disease progression (as defined in sections 5.5.1 and 5.5.2)
- Intercurrent illness that prevents further administration of treatment
- Unacceptable adverse event(s)
- Participant demonstrates an inability or unwillingness to comply with the oral medication regimen and/or documentation requirements
- Participant decides to withdraw from the protocol therapy
- General or specific changes in the participant's condition render the participant unacceptable for further treatment in the judgment of the treating investigator

Participants will be removed from the protocol therapy when any of these criteria apply. The reason for removal from protocol therapy, and the date the participant was removed, must be documented in the case report form (CRF). Alternative care options will be discussed with the participant.

When a participant is removed from protocol therapy and/or is off of the study, the relevant Off-Treatment/Off-Study information will be updated in OnCore.

## 5.5.1 Tumor Response Assessments

Antitumor activity will be assessed through radiological tumor assessments conducted at baseline (screening) of starting therapy and every 2 cycles (6 weeks) thereafter. In addition, radiological tumor assessments will also be conducted whenever disease progression is suspected (eg, symptomatic deterioration) and at the time of withdrawal from the treatment (if not done in the previous 4 weeks). Complete, partial responses and progressive disease must be confirmed on repeated imaging  $\geq$  4 weeks after initial documentation, but not more than 6 weeks after initial documentation.

Assessment of response will be made using RECIST version 1.1 and as per immune-related RECIST criteria (irRECIST).

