#### 6.3 **Re-treatment Criteria**

For a patient to begin a new cycle or continue a cycle of therapy after a dose modification, the following criteria must be met.

- Pre-treatment criteria as described in Section 5.2.2 with the following exceptions
  - $\circ$  Treatment-emergent ocular disorders, which must have recovered to  $\leq$  Grade 1 or baseline
  - $\circ$  Treatment-emergent pneumonitis which must have recovered to  $\leq$  Grade 1

If the patient does not meet these criteria, dosing with the two agents in the combination regimen will be delayed and the patient should be re-evaluated within 48-72 hours. Dosing with both agents may resume if these criteria have been met. If the adverse event can be attributed to one of the agents in the combination regimen, that agent will be held or discontinued as per the Dose Modification Guidelines

described in Sections 6.1 and 6.2 respectively; however, treatment with the second agent may resume provided all the other criteria are met. However, if the next cycle is delayed due to treatment-related toxicity longer than 12 weeks then the patient should be removed from study treatment. In such cases, continuation of study treatment may be considered for those patients who have experienced clinical benefit if agreed upon between the Overall PI and the Investigator.

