#### 13.1 Study Design/Endpoints

#### Primary Endpoints

To assess the activity of mirvetuximab soravtasine in combination with pembrolizumab in patients with recurrent or persistent MSS and FR $\alpha$  positive endometrial cancer by evaluating the frequency of patients who survive progression-free for at least 6 months (PFS6) after initiating therapy or have objective tumor response.

Statistical considerations are developed for co-primary objectives to evaluate the objective response rate (ORR) by RECIST 1.1 and rate of progression-free survival at 6 months (PFS6), with a two-stage design that allows for early stopping for futility.

A two-stage test was constructed using the method of Sill, Rubinstein, Litwin and Yothers [36] with the goal of stopping early for futility to limit patient exposure to an inactive agent while restricting the probabilities of type I and type II errors to approximately 10% and 15%, respectively. For the co-primary endpoints, a true ORR of 5% or less and a rate of progressionfree survival at 6 months of (PFS6) 10% or less would not be of clinical interest (H0:  $\pi_{OR} \leq 5\%$ AND  $\pi_{PFS6} \le 10\%$ ), whereas an improvement to a 20% objective response rate or 30% PFS6 rate would warrant further investigation of the study treatment. In the first stage, 16 patients will be enrolled and accrual will pause. If there are at least two objective responses or two patients progression-free at 6 months among the first 16 patients, the second stage of accrual will commence where an additional 19 patients will be enrolled. If at the end of the trial there are at least 4 treated patients with an objective response or 8 patients progression-free at 6 months, the study treatment will be considered worthy of further study. Specifically, analysis of historical data (GOG129 and GOG229 series) based on similar population of patients with endometrial cancer where the levels of activity were believed to be inactive to modestly active shows that an unacceptable rate for objective response ( $\pi_{OR}$ ) is 5% and for PFS6 ( $\pi_{PFS6}$ ) is 10%, respectively. A bivariate test of the co-primary endpoints is constructed as follows:

H0:  $\pi_{OR} \leq 5\%$  AND  $\pi_{PFS6} \leq 10\%$ 

vs. H1:  $\pi_{OR} > 5\%$  OR  $\pi_{PFS6} > 10\%$ 

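### Scans are counted in treatment cycles and nothing holds them to the calendar when a cycle slips, so the time at which PFS6 is read is not fixed and progression before 6 months can count as a success

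*Combined protocol and SAP*

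**What the plan says.** Section 5.5.1 calls for imaging at baseline and "every 2 cycles (6 weeks) thereafter". It adds imaging whenever progression is suspected, and at withdrawal from treatment unless a scan was done in the previous 4 weeks. The Study Calendar gives the same interval with a tolerance of one week either way. A cycle is 21 days (Section 5.1).

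Delays are allowed. Sections 6.1.3 and 6.2 provide for interruptions of up to 3 weeks for reasons other than treatment-related adverse events. Section 6.3 takes a patient off treatment only "if the next cycle is delayed due to treatment-related toxicity longer than 12 weeks". No section says whether a scan moves when a cycle moves.

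PFS6 is one of two co-primary endpoints (Sections 1.2 and 13.1). Stage 2 opens if there are "at least two objective responses or two patients progression-free at 6 months among the first 16 patients", and the final rule is met by 4 responses or "8 patients progression-free at 6 months" out of 35. Section 13.5 refers back to 13.1. Neither section names the scan that decides PFS6, sets a window for it, or says how to score a missing scan or progression first seen at the following scan. The only dating rule found is for new lesions (Section 11.1.3, New Lesions), which uses the date of the assessment that first showed the lesion.

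**The concern.** On schedule the scans fall at weeks 6, 12, 18, 24 and 30. Six months is 26.09 weeks, and the windows around the fourth and fifth scans (weeks 23-25 and 29-31) do not reach it. A patient who progresses in week 25 without symptoms is first found at week 30 and can be counted as progression-free at 6 months. If scans also move with the cycles, the last look before 6 months falls at a different week for each patient, depending on toxicity and interruptions.

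The decision rule has little room for this. The design aims at "restricting the probabilities of type I and type II errors to approximately 10% and 15%, respectively", its stated alpha under independence is already 0.098, and meeting either endpoint alone declares the regimen worth further study. Any upward shift in the PFS6 rate of an inactive regimen therefore passes straight into the trial's conclusion.

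**Working it through.** **Inputs from the plan (Section 13.1).** The null is "a true ORR of 5% or less and a rate of progressionfree survival at 6 months of (PFS6) 10% or less". The targets are 20% ORR or 30% PFS6. There are 16 patients in stage 1 and 19 more in stage 2. The trial stops if responses R ≤ 1 and PFS6 successes S ≤ 1, and rejects the null if R ≥ 4 or S ≥ 8 of 35.

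**Reproducing Table 12.** Under independence the probability of early termination is Pr(R ≤ 1 | 16, 0.05) × Pr(S ≤ 1 | 16, 0.10) = 0.8108 × 0.5147 = 0.417, as printed. Exact enumeration over both stages gives alpha 0.098 and power 0.889 and 0.873, also as printed. The dependence column is reproduced if the joint probability is 90% of the smaller rate: early termination 0.502, power 0.846 and 0.862, alpha 0.088. The printed dependence alpha of 0.88 is therefore a misprint for 0.088.

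**Assumptions for the check.** The true 6-month rate is 10%, PFS is exponential, and progression after the last scan before 6 months (week w) is dated at the next scan. The apparent null rate is then p(w) = 0.10^(w/26.09). For w = 24 this is 0.10^0.920 = 0.120.

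| Last scan before 6 months | Apparent PFS6 | Type I error, PFS6 rule alone | Overall alpha (independence) |
|---|---|---|---|
| At 6 months (design) | 10.0% | 0.0195 | 0.098 |
| Week 26 | 10.1% | 0.020 | 0.099 |
| Week 25 | 11.0% | 0.033 | 0.111 |
| Week 24 (on schedule) | 12.0% | 0.051 | 0.129 |
| Week 23 | 13.1% | 0.078 | 0.155 |
| Week 21 | 15.7% | 0.168 | 0.240 |
| Week 18 | 20.4% | 0.418 | 0.470 |

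With 90% overlap the week-24 alpha is 0.112, against 0.088. Replacing the exponential by a Weibull with shape 0.8 to 1.5 gives 0.121 to 0.155 at week 24 under independence.

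**Which way delays act.** A total slip of 1 or 2 weeks moves the fourth scan to week 25 or 26, closer to 6 months, and alpha falls to 0.111 or 0.099. A 3-week slip before the first scan gives scans at weeks 9, 15, 21 and 27, so the last look is week 21. A 3-week slip after the week-18 scan leaves week 18 as the last look. The last two table rows apply if every patient slips in that way, so they are bounds and not forecasts. If 30% of patients slip 3 weeks early, the apparent rate is 0.7 × 12.0% + 0.3 × 15.7% = 13.1% and alpha is 0.155.

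**Random delays.** The documents give no delay frequencies, so these are assumed: 10-30% of two-cycle blocks are delayed, with the length spread evenly over the stated range. Overall alpha under independence is:
- 1-week slips: about 0.12, slightly below the on-schedule 0.129.
- 1-3 weeks: about 0.14-0.17 (0.137-0.158 in a second simulation of 1-3 week delays).
- 2-3 weeks: about 0.16-0.20.

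**Unscheduled scans.** If imaging at suspected progression catches half of the between-scan progressions on the week-24 grid, the apparent rate is 11.0% and alpha is 0.111. If it catches all of them, alpha is back at 0.098.

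**The case against.** The strongest reply is that the 10% null is itself an observed rate. Section 13.1 takes it from the GOG129 and GOG229 series. If those trials scanned on a similar grid with similar delays, the shift is already in the benchmark and there is no net inflation. The documents give neither their scan schedules nor their delays, so this can be neither confirmed nor excluded. A reader might infer that the delay part, at least, cannot be in the null. The documents do not support that either.

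A reader might also infer that toxicity delays always make the error larger. They do not, because slips of 1 or 2 weeks bring the fourth scan closer to 6 months. The 12 weeks in Section 6.3 is a limit for removal from treatment, not a typical delay. The same section asks for re-evaluation within 48-72 hours and lets the second agent resume when the toxicity belongs to one drug, although Section 6.2 holds both for immune-related events.

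The Study Calendar's one-week tolerance can be read as tying scans to 6 calendar weeks. That is a fair reading, but the same line also counts in cycles, so sites could follow either. Finally, Section 5.5.1 requires scans at suspected progression, which reduces the effect. Such scans depend on suspicion and can miss silent radiological progression.

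These replies leave the size open. They do not supply the missing anchor for the scans or the missing scoring rule.

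**Conclusion.** The gap in the text is real: scan timing is ambiguous when cycles slip, no scheduled scan or window covers 6 months, and no rule says how PFS6 is scored between scans. The stronger statement, that the trial's type I error is raised, is not established.

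The size is conditional. If the null is a true 26-week rate, PFS is exponential and only scheduled scans find progression, alpha is about 0.13 (independence) or 0.11 (90% overlap) on schedule, against 0.098 and 0.088. Under the assumed delays it is about 0.12 to 0.20 (independence). If the benchmark was read on a similar grid with similar delays, or if unscheduled scans catch every between-scan progression, there is no inflation.

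**What to change.** 1. In Section 5.5.1 and the Study Calendar, schedule scans every 6 weeks (±1 week) counted from Cycle 1 Day 1, regardless of dose delays or interruptions. This removes the dependence on delays. It does not remove the on-schedule week-24 shift, which the next step addresses.
2. In Section 13.1 or 13.5, state the scan schedule behind the 10% and 30% benchmarks and score PFS6 by a rule that matches it. The rule should name the scan that decides PFS6 and say how progression first seen at the next scan, or a missing scan, counts. Report alpha and power under that rule.
3. Move the week-24 scan to 6 months only if the benchmark is a true 6-month rate, and then with a window that does not open before 6 months, since a scan at week 25 still gives alpha 0.111. A reader might take the move as the obvious repair, but it is a trade-off. If the benchmarks were read at week 24, a true target regimen has a PFS6 rate of 0.30^(26/24) = 27.1% at week 26 and 0.30^(27/24) = 25.8% at week 27. Power for the PFS6 alternative then falls from 0.873 to about 0.785 or 0.733, below the planned 85%. The move would also need a written exception to the 6-week interval, because the gap from week 18 becomes about 8 weeks.

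Steps 1 and 2 cost amendment wording and a recalculation of Table 12, with no added scans. The downside is that some scans will not coincide with a dosing visit.
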